Single 24-hour urine collection	Collect within 14 days prior to dosing (M3) or visit (M4, M5, M6); repeat if invalid. See Table 4			х	х	Х	Х			
Blood sample for PD analyses	Section 6.3	X	X	X			X	X	X	
Clinical laboratory assessments	Section 6.5.4	X	X	X			X	X	X	X
Antidrug antibody sample	Section 6.5.4.1		X	X			X	X	X	X
Urine pregnancy test (for WOCBP) c	May be performed more frequently where required per local requirements, or if pregnancy is suspected. See Section 6.5.4.2		х	X				Х		
Symptom-directed physical examination	Section 6.5.3		X	X				X		X
Prior and concomitant medications	Section 5.4		Continuous							

Table 1: Schedule of Assessments

			1	5 Monti Treati	h Doub nent Pe		I			
		Screening	Pri	mary A	nalysis l	Period		Treat Exter Per	nsion	Safety
Study Visit			Baseline	М3	M4	MS	М6	ЕОТ М9	EOS/ ET M15	Follow-up (Patients who D/C Treatment Early)
Study Day (±Visit Window)	Notes	-60 to -1	Day 1	85 (±14)	113 (±7)	(41 (±7)	169 (±14)	253 (±28)	421 (±28)	3 and 6 months post last dose (±28)
Clinical kidney stone events	Section 6.2.2				C	ontinuo	us			
Review/record adverse events	Section 6.5.5				C	ontinuo	us			
Healthcare utilization	Section 6.6				C	ontinuo	us			
Randomization	Window: 1 business day prior to Day 1 for study drug preparation		X							
Blood samples for PK analyses	Table 2; Section 6.4		X							
Study drug administration	Section 5.2.2		X	X				X		
Optional low-dose kidney- protocol CT scan d	Section 6.2.2.2		X (-3 days window)			1 64			X	

Abbreviations: CT=computed tomography; D/C=discontinue; ET=early termination; EOS=end of study; EOT=end of treatment; M=month; PD=pharmacodynamic; PK=pharmacokinetic; WOCBP=women of child-bearing potential Notes:

- When scheduled at the same time points, assessments of vital signs should be performed before physical examinations and blood sample collections, where feasible.
- Patients who discontinue study drug dosing for any reason will be encouraged to remain on the study to complete the remaining assessments so that their experience is captured in the final analyses (refer to Section 4.3.1).

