# 3.3. Justification for Dose

Two dose levels of lumasiran 284 and 567 mg given on Day 1, Month 3, and Month 9 were selected to evaluate urinary oxalate dose response. The higher dose level of 567 mg is expected to suppress GO enzyme by ≥95%, comparable to the regimen evaluated in ALN-GO1-003 (ILLUMINATE-A) in patients with PH1. The lower dose of 284 mg is expected to suppress GO enzyme by 90%. In addition, the fixed doses will simplify dose administration in this adult study population. Both regimens are predicted to achieve near-steady state ribonucleic acid-induced silencing complex (RISC) concentrations and urinary oxalate suppression at Month 6. Month 9 dosing is intended to sustain PD effect through Month 15 and will provide data to differentiate the effect of every 3 months and every 6 months dosing on urinary oxalate reduction.

Single 0.3 to 6.0 mg/kg doses of lumasiran in healthy subjects and multiple 3.0 mg/kg doses of lumasiran administered monthly or once every 3 months in patients with PH1 have been well tolerated. Plasma and liver exposure for the lumasiran 284 and 567 mg doses are expected to be in the range of 3.0 to 6.0 mg/kg lumasiran doses evaluated in healthy subjects in ALN-GO1-001 (Part A) and patients with PH1 in ALN-GO1-001 (Part B), ALN-GO1-002, and ILLUMINATE-A. Based on rat and monkey NOAEL doses of lumasiran 200 mg/kg and 300 mg/kg, a sufficient safety margin exists for the use of lumasiran 284 and 567 mg doses (refer to the ALN-GO1 Investigator Brochure).

Based on a 70 kg patient, the planned doses of 284 mg and 567 mg equate to approximately 4.0 mg/kg or 8.0 mg/kg, respectively. The human equivalent dose (HED) margin values for the

approximate 4 mg/kg clinical dose were 8.1-fold for the chronic rat study and 24.2-fold for the chronic monkey study; the HED margin values for the approximate 8.0 mg/kg clinical dose were 4.0-fold for the chronic rat study and 12.1-fold for the chronic monkey study (refer to the ALN-GO1 Investigator Brochure).

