#### 6.2.1. 24-Hour Urine Collections

Urinary oxalate excretion and calcium oxalate supersaturation (calculated from multiple parameters) will be determined from 24-hour urine sample collections to be completed at the time points specified in the Schedule of Assessment (Table 1). The start and stop dates/times of collection, the volume of urine in the collection, whether there were any missed voids, and whether the patient complied with dietary recommendations will be recorded. An aliquot of the 24-hour urine collection will also be used to determine urinary creatinine content and to determine if the 24-hour urine collections need to be repeated (see Section 6.2.1.1).

The 24-hour urine collection procedure by study visit is provided in Table 4.

Table 4: 24-hour Urine Collection Procedure by Study Visit

Study Visit and Urine Collection Window	Number of Collections to Schedule	Validity Requirement Prior to Dosing/Visit (see Section 6.2.1.1)	Notes
Screening (within 60-day period)	2	2 valid collections prior to dosing unless variability criterion is not met (Section 6.2.1.2), in which case an additional collection is required a .	Supervised collections b are encouraged unless patient is already familiar with the collection procedure. If any collections are invalid, the remaining collections for screening must be supervised.
Months 3, 4, 5, and 6 (within 14 days prior to dosing/visit)	1	No	If an invalid collection is obtained for the timepoint, a single repeat collection must be supervised. Repeat collection, if necessary, is to be completed within ±14 days of dosing/visit.
Months 9 and 15 (within 14 days prior to dosing/visit)	2	1 valid collection prior to dosing/visit	If a patient has had ≥2 prior invalid collections, both collections at these visits must be supervised b . At least 1 valid collection must be obtained prior to dosing/visit. If any collections for the timepoint are invalid, the remaining collection(s) for the timepoint must be supervised.

<sup>a The additional collection is not required to be valid in order to proceed with dosing, but will be tested to confirm validity for the calculation of baseline 24-hour urinary oxalate.

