## 7.2.5. Efficacy Analyses

The hypothesis testing for the primary endpoint will be tested comparing each lumasiran group to the placebo group in the FAS with a 2-sided significance level of 0.05.

The primary endpoint will be analyzed using a mixed-effect model for repeated measures (MMRM) approach. The outcome variable is percent change from baseline in urinary oxalate to Month 6 (average across Months 4 through 6). The model includes baseline 24-hour urinary oxalate and the stratification factor of number of historical kidney stone events (>1 versus ≤1 event in the 12 months prior to screening) as covariates, and fixed effect terms including treatment arm, visit and visit and treatment arm interaction. The estimate of treatment difference for the average percent change from baseline of 24-hour urinary oxalate excretion across Months 4 through 6 will be calculated via a linear contrast of the corresponding coefficients from the MMRM model.

Additionally, the percent change from baseline in 24-hour urinary oxalate excretion at Month 9 and Month 15 will be summarized and compared between lumasiran and placebo treatment groups.

Baseline, Month 9, and Month 15 urinary oxalate values and urinary calcium oxalate supersaturation values are planned to be collected in either duplicate or triplicate (baseline) and duplicate (Months 9 and 15), and the calculated median of valid collections during each time period (visit) will be used in the analysis.

Analysis of secondary endpoints and exploratory endpoints will be specified in the SAP. No multiplicity adjustment is planned.

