4.1. General Considerations

Categorical variables will be summarized using counts and percentages. The percentage will not be presented for a count of zero.

Continuous variables will be summarized using the following descriptive summary statistics: number of patients (n), mean, standard deviation (SD), standard error of the mean (SEM), median, first quartile (Q1), third quartile (Q3), minimum, and maximum. The same level of precision collected in the database will be displayed for the minimum and maximum, plus one additional decimal for the mean and median, plus 2 additional decimals for SD and SEM.

For 24-hour urinary oxalate, urinary calcium oxalate supersaturation, and 24-hour urinary glycolate:creatinine ratios, the median of valid collections will be used as the value at any visit where multiple collections are done because of the variability of these parameters. For other PD parameters, the mean of all assessments will be used if multiple collections are done at a given visit. For safety laboratory parameters, assessments collected and recorded as lower than the LLOQ will be replaced by the LLOQ. Any assessment collected and recorded as greater than the upper limit of quantification (ULOQ) will be replaced by the ULOQ. The day of the first dose of study drug administered is defined as Day 1. The Study Day of a time point of interest is calculated as follows.

If on or after Day 1, Study Day = date of interest – date of the first dose of study drug + 1

If prior to Day 1, Study Day = date of interest – date of the first dose of study drug

There is no Day 0. For example, the day before the first study drug dose is defined as Day -1.

All descriptive summaries will be presented by treatment arm (lumasiran 284 mg, lumasiran 567 mg, placebo) and overall, where applicable. In addition to presentation by treatment arm, a pool of lumasiran 284 mg and 567 mg will also be presented as all lumasiran treatment for the safety analysis.

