5.7.2. Secondary Endpoints

The percentage of patients who achieve a $\geq 20\%$ reduction in 24-hour urinary oxalate from baseline to Month 6 (average across Months 4 through 6) will be analyzed using the Cochran-Mantel-Haenszel (CMH) test stratified by the 2 stratification factors (Section 4.5). The odds ratio with the corresponding 95% CI and associated p-value will be presented. In addition, the differences in proportion of responders and corresponding 95% CI using the Newcombe method based on the Wilson score will also be presented. In addition, a tabulation and a bar chart showing the proportion of patients with a $\geq 20\%$ reduction in 24-hour urinary oxalate from baseline to each visit and on average across Months 4 through 6 will be presented.

For the analysis of urinary calcium oxalate, selected medication could potentially impact the endpoint, therefore the assessments will be excluded from analysis if patients start, stop, or change any of the following medications within a specified time frame of the data collection:

- Vitamin C equivalent to ≥500 mg in a single day is taken at any point within 4 days prior to the start of or during the urine collection (see Table 2)
- The patient is on a new daily dose (relative to screening) of hydrochlorothiazide, allopurinol, topiramate, acetazolamide or furosemide at any point within 4 days prior to the start of or during the collection
- Urine alkalinization agents (potassium citrate, potassium citrate-citric acid, sodium citrate-citric acid, sodium citrate-potassium citrate-citric acid, sodium bicarbonate, potassium bicarbonate, or potassium bicarbonate-potassium citrate) started, stopped, or changed at any point within 2 days prior to the start of or during the collection (relative to screening)

Percent change in urinary calcium oxalate supersaturation from baseline to Month 6 (average across Months 4 through 6) will be analyzed using the same MMRM approach as for the primary endpoint. Descriptive statistics will also be generated for the actual values, change from baseline, and percent change from baseline at each scheduled visit by treatment arm. LS Mean (+/- SEM)

figures of percent reduction by treatment arm will be plotted as well as individual spaghetti plots. Listings will also be generated.

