5.8. Pharmacodynamic Analyses

The PD parameters include plasma oxalate, plasma glycolate, 24-hour urinary glycolate:creatinine ratios, and spot urinary oxalate:creatinine ratios. Summary tables, mean (+/-SEM) figures, and individual spaghetti plots will be provided for observed values, absolute changes, and percentage changes from baseline for each scheduled time point by treatment group. FAS is used for all PD parameters except for plasma oxalate where a separate analysis population, Plasma Oxalate Analysis Set is used.

The number and percent of patients with 24-hour urinary oxalate \leq ULN (40 mg) and the number and percent of patients having a 25% reduction in urinary calcium oxalate supersaturation will be presented over time.

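### The over-time percentages for oxalate ≤ULN and 25% supersaturation reduction rest on one urine collection at Months 3–6 but on up to two at Months 9 and 15, so they are not comparable across the Month 6 to Month 9 step

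*SAP*

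**What the plan says.** **Collections per visit.** Protocol Table 4 (section 6.2.1) schedules one 24-hour collection at each of Months 3, 4, 5 and 6. The Schedule of Assessments agrees: "Collect within 14 days prior to dosing (M3) or visit (M4, M5, M6); repeat if invalid". Table 4 adds: "If an invalid collection is obtained for the timepoint, a single repeat collection must be supervised". A repeat follows only an invalid collection, so at most one valid value is planned per visit. At Months 9 and 15 two are scheduled, of which at least one must be valid.

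**Visit value.** Protocol 7.2.5 describes collection in "duplicate (Months 9 and 15), and the calculated median of valid collections during each time period (visit) will be used in the analysis". SAP 4.1 has the same rule for oxalate and supersaturation: "the median of valid collections will be used as the value at any visit where multiple collections are done". It gives the variability of these measures as the reason. The median of two values is their mean.

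**What is shown.** SAP 5.8 presents the percentage with oxalate ≤ULN (40 mg) over time, and states that "the number and percent of patients having a 25% reduction in urinary calcium oxalate supersaturation will be presented over time". SAP 5.7.3 extends the exploratory summaries to the 15-month double-blind period. For the ≥20% oxalate response, SAP 5.7.2 plans a tabulation and bar chart in which "reduction in 24-hour urinary oxalate from baseline to each visit and on average across Months 4 through 6 will be presented", without naming Months 9 and 15.

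Neither document equalises the number of collections across visits, adds a single-collection summary, or tells the reader that the number changes.

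**The concern.** A percentage below a fixed cut-off depends on the spread of the scored value as well as on its centre. Patients enter with two screening collections above 40 mg, so many placebo values at or below 40 mg will be chance crossings, and averaging two collections removes some of them. The percentages can then step between Month 6 and Month 9 although no patient's true excretion has changed.

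The step falls at an awkward place. Month 6 is three months after the Month 3 dose and Month 9 is six months after it. Protocol 3.3 says that the Month 9 dose "will provide data to differentiate the effect of every 3 months and every 6 months dosing on urinary oxalate reduction". Someone reading a response-rate table or chart across Month 6 to Month 9 would be comparing two scoring rules as well as two times since dosing.

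**Working it through.** **1. The plan's own figure.** The documents give no figure for the threshold percentages. They do give an SD of percent change, so I first checked how it is used. With SD 45, difference 30 and n = 40 per arm, SE = 45 × √(2/40) = 10.06 and 30/10.06 = 2.98. Two-sided t power with 78 df is 83.8%, against 84% stated. The other five cells of the power table also reproduce to within one point.

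**2. Mechanism.** Let s be the SD of percent change on one collection, f the share of that variance that is collection noise, and ρ the correlation of this noise between the two collections of a visit. Then

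SD with two collections = s × √(1 − f(1 − ρ)/2).

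The documents give s (25, 30 or 45%) but not f or ρ.

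**3. Hand example.** Take s = 45, f = 0.5, ρ = 0, true change 0% on placebo and −30% on lumasiran at every visit. The SD with two collections is 45 × √0.75 = 39.0.

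| Cut-off | Collections | Placebo | Lumasiran | Difference |
|---|---|---|---|---|
| ≥20% reduction | one | Φ(−20/45) = 32.8% | Φ(10/45) = 58.8% | 26.0 |
| ≥20% reduction | two | Φ(−20/39.0) = 30.4% | Φ(10/39.0) = 60.1% | 29.7 |
| ≥25% reduction | one | Φ(−25/45) = 28.9% | Φ(5/45) = 54.4% | 25.5 |
| ≥25% reduction | two | Φ(−25/39.0) = 26.1% | Φ(5/39.0) = 55.1% | 29.0 |

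The difference rises by 3.8 and 3.5 points (unrounded) with a constant drug effect. For f from 0.25 to 0.75 and s of 45, 30 or 25, the ≥20% difference rises by 1.7–6.4, 2.3–8.6 or 2.6–9.4 points. The 25% rows use the oxalate SD; applying them to supersaturation is an assumption.

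**4. Simulation with the plan's rules.** Entry requires both collections >40 mg. A third is taken if variability exceeds 20%, and baseline is the median of the two or three. Assumed: lognormal patient levels with between-patient CV 25%; within-patient CV 20–37%; independent collections; every patient with two valid collections at Months 9 and 15; constant effect. With population medians of 42 and 50 mg, the placebo percent-change SD is 23–43%, close to the plan's 25–45%.

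| Population median | Effect | Shift in ≤ULN difference, one to two collections |
|---|---|---|
| 42 or 50 mg | 30% | about +4 to +8 points |
| 60 mg (mean baseline about 65–68 mg) | 30% | about 0 to +1.6 |
| 60 mg | 20% | −1.6 to −0.4 |

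The ≥20% difference rises by about 8 to 10 points at medians of 42 and 50 mg with a 30% effect. Example (CV 20%, median 42 mg, 30% effect, ≤ULN): placebo 19% to 14%, lumasiran 69% to 70%, difference 49 to 56 points. Placebo rates fell in every scenario. Mean percent change did not move: in this example it was −2.4% on placebo and −31.7% on lumasiran under both rules.

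**5. Less favourable assumptions.** With ρ = 0.3, 25% of patients having one valid collection at Months 9 and 15, and a between-patient response CV of 15%, the shifts at medians 42 and 50 mg and a 30% effect fall to about +1.5 to +3 points (≤ULN) and about +3 points (≥20%).

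**6. Scale.** For 19% against 69% with 40 per arm, SE = √(0.19 × 0.81/40 + 0.69 × 0.31/40) = 9.6 points. For 33% against 59% it is about 11 points. The largest shifts are about one SE; most are well below.

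**The case against.** The case for leaving the plan alone is substantial, and most of it stands as a limit on the point.

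- **Direction.** Widening is not general. Where both arms' typical values lie on the same side of the cut-off, both rates fall and the difference barely moves or narrows.
- **Size.** The larger shifts need independent collections and two valid ones for everyone. Both collections fall within the same 14 days, and Table 4 requires only one to be valid.
- **Supersaturation.** No SD is given, so no size can be put on that measure.
- **The ≥20% chart.** The response belongs to a secondary endpoint defined over Months 4–6. That its by-visit display includes Months 9 and 15 is only a possible reading.
- **Role.** These are descriptive percentages without a test or decision rule. At any one visit all arms are scored alike, and Months 3–6 are mutually comparable.
- **The median** is specified in the protocol, for a good reason.

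A reader might go further and infer that the plan would make lumasiran look durable and hide waning under six-month dosing. A case can be built: if the true effect fell from 30% to 25% at Month 9, a like-for-like fall of 6–10 points in the ≤ULN difference could appear as about 0–8. But the 5-point loss is chosen, and it is about the size of the artefact. Protocol 3.3 speaks of oxalate reduction, and Protocol 7.2.5 compares arms at Months 9 and 15 on percent change, which is unaffected. The documents do not rest the durability question on these percentages.

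What the objections do not remove is the non-comparability itself: one series, two scoring rules, and no notice to the reader.

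**Conclusion.** The point holds for the ≤ULN and 25% supersaturation percentages in SAP 5.8 when they are read across Month 6 to Month 9. It extends to the by-visit ≥20% display in 5.7.2 only if that display includes Months 9 and 15.

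For oxalate, the difference between arms moves by about 0 to 10 points under the assumptions shown, typically upward at a 30% effect, with the exceptions above. The size rests on within-patient variability, correlation between paired collections, the share of patients with one valid collection, and baseline level; the documents give none of these. It would be wrong to infer that the bias always favours lumasiran. The primary endpoint and the Months 4–6 secondary endpoints use no Month 9 or 15 value, and mean changes do not depend on the number of collections averaged. This is a modest, cheaply removed flaw in descriptive outputs.

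**What to change.** In SAP 5.8, and in the by-visit ≥20% display of 5.7.2 if it runs past Month 6:

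- Keep the median-of-valid-collections percentage at Months 9 and 15, as Protocol 7.2.5 specifies.
- Add a row at those visits scored on the first valid collection.
- Use that row for any comparison with Months 3–6, or say in a footnote that only that row is comparable.
- State the number of collections behind the value at each visit.

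Scoring every compared visit on one collection removes the artefact by construction and needs no new data. The cost is a sentence in the SAP and one extra row per table, noisier because it uses one of the two collections. Replacing the median as the main score is not advised: it would depart from the protocol and discard planned data. The primary MMRM and the continuous summaries need no change.

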5.9. Pharmacokinetic Analyses

Plasma lumasiran concentrations by visit will be summarized descriptively for the PK Analysis Set.

5.10. Anti-Drug Antibodies

The number and percentage of patients with confirmed positive anti-drug antibody (ADA) assay results at baseline and at any post-baseline visit during the 6-month primary analysis period, as well as treatment-emergent ADA during the 6-month primary analysis period, will be summarized and listed for the Safety Analysis Set. The same summary and listing will also be done for the Month-15 DB period.

Treatment-emergent ADA consist of treatment-induced ADA and treatment-boosted ADA, as defined below:

- Treatment-induced ADA: Confirmed positive ADA developed de novo after drug administration in patients without preexisting (baseline) confirmed positive ADA
- Treatment-boosted ADA: Confirmed positive ADA after drug administration with ADA titer > 4x baseline ADA titer in patients with preexisting (baseline) confirmed positive ADA

5.11. Safety Analyses

Safety analyses will compare both doses of lumasiran combined and separately versus placebo using the Safety Analysis Set.

5.11.1. Adverse Events

Adverse events (AEs) will be classified by the MedDRA coding system (version 24.1) and displayed in tables and data listings using SOC and PT.

Treatment-emergent AEs (TEAEs) will be summarized, where TEAE is defined as any AE occurring or worsening on or after the first dose of study drug and through 168 days after the last dose or any study drug-related AE. Because any worsening AE is reported as a new AE with higher severity, programmatical comparison of severity is not needed for the classification of TEAE. For missing or partial dates for AEs, the imputation of start and end date can be found in Section 7.3. Events with a fully or partially missing onset date will be assumed to be treatment emergent unless it can be unequivocally determined (from the partial onset date and/or a partial or complete stop date) that the event occurred prior to the first dose of study drug. All TEAEs hereafter will be referred to as AEs in this document.

AEs will be summarized by the numbers and percentages of patients reporting a given AE. An overall table of TEAEs will include, but not limited to:

- At least 1 AE
- At least 1 drug related AE
- At least 1 severe AE
- At least 1 drug related severe AE
- At least 1 Serious Adverse Event (SAE)
- At least 1 drug related SAE
- At least 1 AE leading to treatment discontinuation
- At least 1 AE leading to drug interruption
- At least 1 drug related AE leading to treatment discontinuation
- At least 1 AE leading to study withdrawal
- At least 1 drug related AE leading to study withdrawal
- Death (based on SAE CRFs)

Tabulations by SOC and PT will be produced for the following:

- AEs,
- Treatment-related AEs,
- AEs by maximum severity,
- Treatment-related AEs by maximum severity,
- Severe AEs,
- Treatment-emergent SAEs,
- AEs leading to treatment discontinuation.

Tabulations by PT in decreasing order in frequency within each treatment arm will be produced for the following:

- AEs
- Treatment-related AEs
- SAEs

AEs and AEs related to treatment will also be summarized by severity. A patient contributes only once to the count for a given AE (overall, by SOC, by preferred term). Patients who report multiple occurrences of the same AE (preferred term) will be classified according to the most severe occurrence. An AE with missing severity will be assumed to be severe. An AE with missing study drug relatedness will be assumed to be related.

Listings of all deaths, SAEs, and AEs leading to treatment discontinuation will be provided.

Selected AE tabulations will include number of AEs and event rates per patient-year. In these summaries, multiple occurrences of the same AE in a patient will be counted multiple times for that patient.

AE summary tables (by SOC and PT) will be separately generated for each of the subgroups below:

- Sex (Male, Female)
- Race (White, Black, All other)
- Region (US, Europe)

AEs of Clinical Interest

The following AECI will be summarized by SOC and PT:

• Severe or serious injection site reactions (ISRs): AEs mapping to the HLT "Injection Site Reactions" using MedDRA dictionary.

A tabulation will also be generated to display the number of patients with at least 1 ISR, total number of doses (any dose split into multiple injections will be considered 1 dose in summary), total number of doses with ISRs, and the signs and symptoms reported due to ISRs. If there are multiple ISRs that occur in between 2 consecutive injections, then these events will be considered as 1 ISR and considered related to the earlier injection.

• ALT or AST >3xULN: AEs mapping to certain standardized MedDRA queries (SMQs) will be summarized by SOC and PT.

All AEs will be presented in patient data listings. AEs mapping to the SMQs as described above will also be listed.

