#### **Adverse Event Severity**

Adverse events are to be graded according to the categories detailed below:

Mild:	Mild; asymptomatic or mild symptoms; clinical or diagnostic observations only; intervention not indicated.
Moderate:	Moderate; minimal, local or noninvasive intervention indicated; limiting age appropriate instrumental activities of daily living (eg, preparing meals, shopping for groceries or clothes, using the telephone, managing money).
Severe:	Severe or medically significant but not immediately life-threatening; hospitalization or prolongation of hospitalization indicated; disabling; limiting self-care activities of daily living (ie, bathing, dressing and undressing, feeding self, using the toilet, taking medications, and not bedridden); OR life-threatening consequences; urgent intervention indicated; OR death related to an AE.

Changes in severity should be documented in the medical record to allow assessment of the duration of the event at each level of severity. Adverse events characterized as intermittent require documentation of the start and stop of each incidence. When changes in the severity of an AE occur more frequently than once a day, the maximum severity for the experience that day should be noted. If the severity category changes over a number of days, then those changes should be recorded separately (with distinct onset dates).

Adverse event severity and seriousness are assessed independently. 'Severity' characterizes the intensity of an AE. 'Serious' is a regulatory definition and serves as a guide to the Sponsor for defining regulatory reporting obligations (see definition for SAE).

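### Severity records of one continuing AE are never linked, so selected event-count tables can count it more than once and an improving screening SAE can be flagged treatment-emergent

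*SAP*

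**What the plan says.** **Recording.** The Adverse Event Severity part of Protocol 6.5.5.1 says: "If the severity category changes over a number of days, then those changes should be recorded separately (with distinct onset dates". No direction is given, and the stated aim is to show how long the event lasted at each severity, which requires falls as well as rises to be recorded. Changes more frequent than once a day are reduced: "the maximum severity for the experience that day should be noted". Intermittent AEs are to have the start and stop of each incidence documented.

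**Pre-dose events.** Under Protocol 6.5.5.2, non-serious events between consent and first dose go to medical history and become AEs only if they worsen after dosing. SAEs are recorded from consent.

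**Treatment-emergent flag.** SAP 5.11.1 defines a treatment-emergent AE as "any AE occurring or worsening on or after the first dose of study drug and through 168 days after the last dose", or any drug-related AE. It adds: "Because any worsening AE is reported as a new AE with higher severity, programmatical comparison of severity is not needed for the classification of TEAE".

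**Counting.** Patient-level tables count each patient once: "A patient contributes only once to the count for a given AE (overall, by SOC, by preferred term". For events: "Selected AE tabulations will include number of AEs and event rates per patient-year", and "In these summaries, multiple occurrences of the same AE in a patient will be counted multiple times for that patient". The SAP does not define an occurrence.

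**The concern.** The recording rule and the counting rule do not fit together. The protocol can give one continuing event several onset dates, and the SAP counts multiple occurrences without saying whether a severity segment of a continuing event is one. Read as written, an episode contributes as many events as it has severity segments. The tables affected would then measure how often severity changes as well as how often AEs happen.

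The treatment-emergent flag depends on the same records. The SAP treats a new record as proof of worsening, but the protocol's rule also covers a fall in severity. For an SAE already in the data before dosing, a fall after Day 1 can create a record with a post-dose onset, and the SAP has removed the check that would show it to be an improvement.

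AE frequency is the safety endpoint and arms have about 40 patients, so a few split or misflagged events are visible.

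**Working it through.** The documents state no AE count or rate, so there is no figure to reproduce. The check sets the rules side by side and then sizes the effect under stated assumptions.

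**Step 1: events from one episode that starts after dosing.**
- Mild to moderate on different days: two records. The SAP itself calls the worsening a new AE, so this case does not depend on how the protocol's rule on falls is read.
- Mild, moderate, mild on different days: three records, because the protocol's rule covers both directions.
- Changes within one day: one record for that day, at its maximum severity.

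**Step 2: is there a rule that collapses them?**
- Kidney stone events (Protocol 6.2.2): yes. Only the highest grade is reported, and they are not AEs.
- Injection site reactions (SAP 5.11.1): yes, but only in their own tabulation, where several between two consecutive injections count as one.
- Patient-level AE tables (SAP 5.11.1): yes. Each patient counts once, at the most severe occurrence.
- General event counts and rates per patient-year: no rule.

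**Step 3: size of the overcount.** Let p be the share of episodes whose severity changes across days and k the number of changes in each such episode. Both are assumed.

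Records per episode = 1 + p × k.

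For scale, assume 40 patients followed 421 days (the Month 15 study day): 40 × 421 / 365.25 = 46.1 patient-years. With an assumed 100 true episodes, the rate is 100 / 46.1 = 2.17 per patient-year.

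| p | k | Factor | Counted events | Rate per patient-year |
|---|---|---|---|---|
| 0.10 | 1 | 1.10 | 110 | 2.39 |
| 0.10 | 2 | 1.20 | 120 | 2.60 |
| 0.20 | 1 | 1.20 | 120 | 2.60 |
| 0.20 | 2 | 1.40 | 140 | 3.04 |
| 0.30 | 1 | 1.30 | 130 | 2.82 |
| 0.30 | 2 | 1.60 | 160 | 3.47 |

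With one count per episode, the factor is 1.00 in every row.

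**Step 4: an SAE that starts in screening.**
1. It is recorded, because SAE recording starts at consent.
2. It is still present at Day 1 and becomes less severe some days later.
3. The protocol's rule gives the lower severity its own onset date, which is after the first dose.
4. The SAP makes no severity comparison, so the onset date decides, and the record is flagged treatment-emergent and serious.
5. The patient enters the treatment-emergent SAE tables, including patient-level ones. One such patient in an arm of 40 adds 1 / 40 = 2.5 percentage points.

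An improving non-serious pre-dose event fails at the first step: it stays in medical history and produces no AE record.

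**The case against.** The strongest reply is that the documents never order a double count. The protocol describes one event with several severity levels and asks for the changes to be recorded separately; it does not call each change a new AE. The SAP counts occurrences, not records, and a segment of a continuing event need not be an occurrence. The eCRF completion guidelines, which are not available here, may settle how segments are entered. This stands in part: the overcount comes from a missing rule, not an explicit instruction. But the SAP does say that a worsening is reported as a new AE, and it offers nothing to join that record to the earlier one.

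A second reply concerns the screening SAE: an event that continues and improves neither occurs nor worsens after dosing, so it falls outside the definition. That is the sensible intent, but the SAP tells the programmer not to compare severities, and onset date alone cannot tell improvement from worsening. The case is narrow, since screening lasts at most 60 days and kidney stone events are not captured as SAEs.

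Three stronger readings are tempting and not supported.
- *Every severity change opens a record.* Same-day changes do not.
- *Any improving pre-dose event can become treatment-emergent.* Only SAEs can, because non-serious events go to medical history unless they worsen.
- *The comparison between arms is biased.* If 30% of AEs on lumasiran and 10% on placebo split once, equal true rates would give an apparent ratio of 1.3 / 1.1 = 1.18; if the 30% split twice, 1.6 / 1.1 = 1.45. But no AE rate ratio or test is planned, the fractions are assumptions, the recording rule is the same in every arm, and site personnel are in general blinded. The figures only illustrate what unequal splitting would do.

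**Conclusion.** The point holds within limits. One continuing AE can be counted two or more times in the selected descriptive tables of event counts and rates per patient-year. Under the assumed 10% to 30% of episodes with one or two severity changes, the inflation is 10% to 60%; the true figure cannot be derived from the documents. Splitting can only raise these counts, and it leaves the number and percentage of patients with an AE unchanged.

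The treatment-emergent misclassification is a separate and rarer fault, confined to SAEs that begin between consent and first dose and improve afterwards. It does reach patient-level tables. Here the SAP states a premise that the protocol does not support, so this goes beyond missing detail. Neither fault touches the efficacy analyses. Both should be corrected because AE frequency is the safety endpoint and the correction is cheap.

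**What to change.** In SAP 5.11.1:

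1. For event counts and rates, link records in the same patient with the same preferred term and different severity when the later onset falls on, or the day after, the earlier end date. Do not link AEs recorded as intermittent with separate start and stop dates.
2. Count the linked episode once, at its maximum severity and first onset.
3. Class an episode with pre-dose onset as treatment-emergent only if its severity rises above the pre-dose level after the first dose, or if it meets the SAP's existing drug-related criterion. Remove the statement that no severity comparison is needed.

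The cost is SAP wording and a short linking step in the AE dataset, with no new data collection. There are two downsides. Separate episodes that abut and differ in severity may occasionally be merged. The link also needs AE end dates: SAP 5.11.1 points to Section 7.3 for start and end date imputation, but 7.3 gives AE rules for onset only, so the SAP should also say how a record with a missing end date is handled.
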